6.2 FIDELITY

6.2.1 INTERVENTIONIST TRAINING AND TRACKING

We will hold staff training sessions led by team experts to ensure accurate and complete data collection, storage, transportation, processing, and analyses (e.g., questionnaires, plaque collection). We will have backup plans to ensure data collection in case unanticipated problems arise (for instance, paper forms instead of REDCap[™] for survey data collection due to internet issues). Participant-level checklists will be used to ensure that all necessary data elements are collected at each data collection visit. All data documents will be reviewed for completeness within 24 hours so that relevant corrections or unintentionally missing data can be collected. Data accuracy will be confirmed at the level of data collection by the CTRA. Any staff with

consistent quality issues concerning data collection will receive feedback and be re-trained, as necessary. Staff training will include hands-on training, practice sessions, validation exercises to ensure accuracy, and certification. The CTRA will provide ongoing feedback to data collectors regarding data quality.

6.3 MEASURES TO MINIMIZE BIAS: RANDOMIZATION AND BLINDING

A block-level randomization scheme with a 1:1 allocation ratio will be used to determine interventions for individuals. Random block sizes of 2, 4, and 6 will be used to create the randomization scheme. Randomization will be stratified on primary language and site to ensure balance between the intervention groups. Subjects, clinical examiners, and data analyst will be blinded with respect to treatment allocation; care will be taken to maintain allocation concealment. However, the study CTRA and RAs will not be blinded so that they can deliver the assigned intervention as a supervised exposure to prevent contamination, as a further measure to ensure rigor and transparency. In addition, the study statisticians will be not be blinded in order to manage the dataset, check randomization, check the REDCapTM, etc.

6.4 STUDY INTERVENTION/EXPERIMENTAL MANIPULATION ADHERENCE

When the participating pregnant WIC mother is randomly assigned to one of the two study groups through a randomization algorithm conducted through REDCapTM, based on her language preference (English vs. Spanish), the subject will be linked to her assigned group and study activities in all time points throughout the duration of the study. In addition, the Data Base Manager and CTRA will keep a separate electronic log and verify any potential compliance issues through monthly data reports created by REDCapTM.

Participants will complete pre- and post-intervention questionnaires via REDCapTM at each of the four study visits at the WIC sites. In addition, participants will be sent links with follow-up questionnaires at one and nine months after each visit via texts/emails through REDCapTM. Mother's will have up to eight weeks to complete the one- and nine-month questionnaires. REDCapTM will send reminder text messages and emails at one week, two weeks and three weeks for non-responders of the one- and nine-month questionnaires. If mothers do not complete the questionnaires after the first three reminders, REDCapTM will notify the study team, and an RA will contact the mother to complete the questionnaires. Non-responders will also be mailed paper copies of the questionnaires with a prepaid and self-addressed envelope to return once completed.

It is mandatory that study subjects participate in the first visit at the WIC site for enrollment, informed consent and randomization. In addition, in order to participate in all post-intervention activities (i.e., one- and nine-month questionnaires and 3-month booster message), it is mandatory that subjects complete the assigned group intervention activities at the WIC site visit. For example, if a study subject misses a WIC site intervention (visits 1, 2 or 3), they will not complete the post-intervention activities related to the missed visit but will be scheduled for the next WIC site time point intervention.

Birth to Three – Cavity Free: Effectiveness of a Psychoeducational Intervention for ECC Prevention Protocol

Version 0.7 2 July 2024

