The central hypothesis is that a theory-based intervention approach using videotaped messages and targeted to mothers of high-risk young children will promote an elevated sense of perceived autonomy, competence, and relatedness, which will in turn lead mothers to experience and demonstrate improved self-reported knowledge, behavioral intention and subsequent behavior concerning their child's oral health. Consequently, their child will have more positive oral health outcomes, such as lower levels of caries, dental plaque, and MS. We predict that the theory-based intervention will enhance mothers' oral health care knowledge (Hypothesis 1) and behavior toward their oral health and their child's oral health (Hypothesis 2), relative to neutral messages, also delivered via videotapes. In addition, these hypothesized benefits will apply to both short-term (one-month) and long-term (nine-month) effects across each time point (prenatal, Age 1-2, Age 2-3, Age 3+).

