women (after the women give permission for sharing the information). The WIC staff will then forward this information to study staff who will call the mothers directly to 1) provide a brief overview of the study and introduce the potential risk and benefits of participation, 2) determine interest in study participation, and 3) if they are interested, schedule an initial appointment, at which time formal enrollment will take place and informed consent obtained. The study brochures and posters will be placed at the WIC sites will provide a QR code linking to a contact sheet that mothers can directly fill out to allow study team members to follow-up and contact them.

In order to increase retention, every attempt will be made to maintain contact with all study participants during the clinical trial period through bi-annual study newsletters, multiple phone calls, texts, and emails, along with personal cards to provide valuable communication and continued support with the participants (i.e., congratulate mothers on the baby's birth, mother's and child's birthdays, Mother's Day, thank you notes, etc.). We will create social media contacts through a Birth to Three Cavity Free Facebook study account, and ensure all participants are sent individual, direct messages to prevent information sharing between participants. All of these efforts are crucial to maintaining our cohort of participants.

For all study participants, phone, text, email and/or mail contacts will be made to schedule forthcoming assessment appointments and keep participants engaged in the study. Contacts will include newsletter with updates about the study, as well as thanking the participants. In order to enhance continuing participation in this study, the participants will be verbally encouraged to combine their regular WIC appointments with their visits for this study. In addition, a phone call and text message through REDCapTM (Research Electronic Data Capture) will occur to every participant one week prior to each scheduled appointment to remind them about the time and location, as well as a text message a day before to confirm their appointment attendance. If a WIC appointment is missed, mothers will be allowed up to 2 months to reschedule any of the inperson WIC site visits. If mother's misses the 2-month time window, she will not be able to continue the follow-up questionnaires until the next yearly WIC visit.

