7.3 LOST TO FOLLOW-UP

A study WIC mother will be considered lost to follow-up if she is unable to be contacted by the study team to schedule and participate in their WIC site visit activities at year 2, 3 or 4. If participants miss WIC site visits 2 and/or 3, they can still return to the consecutive WIC site visit(s) but will not complete the post-intervention activities (1- and 9-month follow-ups and 3-month booster message) related to missed WIC site visit(s). The study will not replace lost or withdrawn participants.

The following actions must be taken if a participant fails to return to any of the WIC site visits:

• The study team will attempt to contact the participant, reschedule the missed visit within two months, counsel the participant on the importance of maintaining the assigned visit

schedule and ascertain if the participant wishes to and/or should continue in the study; and

• Before a participant is deemed lost to follow-up, the investigator or designee will make every effort to regain contact with the participant (where possible, three text messages, emails and telephone calls and, if necessary, a letter to the participant's last known mailing address). These contact attempts will be documented in the participant's study file.

Should the participant continue to be unreachable, she will be considered to have withdrawn from the study with a primary reason of lost to follow-up.

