9.3 POPULATIONS FOR ANALYSES

Our primary population for analyses will be the intention-to-treat population. For a sensitivity analysis, the per-protocol population will also be considered. The per-protocol dataset includes subjects who complete the three visits and answer 'yes' to watching all booster messages.

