9.4.3 ANALYSIS OF THE SECONDARY ENDPOINT(S)

Secondary efficacy

Secondary outcomes of interest include changes in knowledge and oral health behaviors of mothers, as well as plaque and microbial outcomes in children. Knowledge outcomes will be measured pre and post intervention via the score on the knowledge assessment. These measures will be considered as counts. GEE modeling will be used with Poisson or negative binomial distributions considered. Results will be presented as incidence rate ratios and 95% confidence intervals.

Maternal change in behavior will be assessed via a set of behavioral questions asked at multiple time points. Each individual question will be dichotomized into improved vs. did not improve based on the answers given pre and post intervention. When analyzing single time points, logistic modeling will be used. To evaluate behavioral changes over time, GEE models with a logit link function will be used. Results will be presented as odds ratios and 95% confidence intervals.

Visible plaque will be analyzed as the number of maxillary and mandibular incisors and molars with plaque at each visit. Analysis of plaque outcomes will focus on Poisson and/or negative binomial modeling, possibly with variance inflation and zero inflation accommodation, as appropriate. To account for repeated longitudinal measurements, GEE will be used to model these counts. Results will be presented as incidence rate ratios and 95% confidence intervals.

Levels of salivary MS will be reported as numbers of bacteria from each visit. Log transformation will be considered if data is skewed, and GEE models assuming a normal distribution with an identity link will be used when analyzing multiple time points. Results will be presented as adjusted least squares means estimates and 95% confidence intervals.

The same covariates as the primary endpoint will be used for both bivariate and multivariable modeling, subject to the constraint of 10 observations/events for every covariate included. Missing data may be addressed via multiple imputation. An AR(1) correlation structure will be assumed for all longitudinal models. QIC will be used for all model/covariate selection involving GEEs; AIC will be used for models calculated for single time points. Mediation analyses will proceed via Baron and Kenny's⁷⁴ steps for mediation analysis and significance will be calculated via Sobel tests.

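### The 1- and 9-month questionnaires after videos 2 and 3 are withheld from mothers who missed that video but stay in the study, so those comparisons are conditioned on adherence, contrary to the stated intention-to-treat population

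*Protocol*

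**What the plan says.** Section 6.4 sets a condition for the 1- and 9-month questionnaires and the 3-month booster: "it is mandatory that subjects complete the assigned group intervention activities at the WIC site visit". For a mother who misses one of visits 1 to 3, it adds that "they will not complete the post-intervention activities related to the missed visit but will be scheduled for the next WIC site time point intervention".

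Section 7.3 applies the same rule to mothers who miss Visit 2 or 3 and makes clear that they are not lost to the study: "they can still return to the consecutive WIC site visit(s) but will not complete the post-intervention activities". Section 5.5 says of a mother who does not reschedule within the two-month window that "she will not be able to continue the follow-up questionnaires until the next yearly WIC visit".

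Section 4.1 places the knowledge and behavior hypotheses at these same times: "these hypothesized benefits will apply to both short-term (one-month) and long-term (nine-month) effects across each time point". Section 8.1 lists maternal knowledge and oral health behaviors as secondary outcomes. Section 9.3 states: "Our primary population for analyses will be the intention-to-treat population". For the secondary endpoints, section 9.4.3 says: "Missing data may be addressed via multiple imputation".

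**The concern.** The rule puts two different things behind one gate. The booster video is intervention, and withholding it after a missed visit is a matter of intervention delivery. The 1- and 9-month questionnaires are outcome measurement. Gating them on attendance means that, in the second and third cycles, an outcome is recorded only if the mother received the video after randomization.

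The protocol expects mothers with such gaps. Section 4.3 accepts the first and last visits as enough for evaluable primary-outcome data. A mother who attends only those two is evaluable for caries, yet loses four questionnaire rounds because of the rule, not because she could not be reached or declined.

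At stake are the short- and long-term contrasts for knowledge and behavior after videos 2 and 3. As observed, they compare mothers who attended that visit in one arm with mothers who attended it in the other. That is not the effect of assignment. Answers that were never requested cannot be recovered at the analysis stage.

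**Working it through.** **The plan's own figures.** The protocol gives no sample size, power or missing-data figure for the knowledge and behavior outcomes. Its caries sample size reproduces and does not depend on this rule. For a difference of 1.1, SD 3.45, 80% power and alpha 0.05 (two-sided assumed), the normal approximation gives 155 per group and the t-based solution 155.4, rounded up to the stated 156. Retention is 317 × 0.79³ = 156.3.

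**Step 1: count the gated assessments.** The inputs are the Schedule of Activities (section 1.3), the order of procedures in section 6.1.2 and the study procedures table. Visit 1 knowledge is measured before the first video and is the baseline, so it is not counted.

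| Post-randomization assessments | Knowledge | Child behavior |
|---|---|---|
| 1 and 9 months after Visit 2 (gated on video 2) | 2 | 2 |
| 1 and 9 months after Visit 3 (gated on video 3) | 2 | 2 |
| After Visit 1 (gated on video 1) | 2 | 1 |
| At Visits 2, 3 and 4 (no video gate) | 3 | 3 |
| Total | 9 | 8 |

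Randomization and video 1 take place at the same visit, so the Visit 1 gate excludes almost no randomized mother. At Visits 2 and 3 the questionnaires are completed before that visit's video, and Visit 4 has no video, so none of these three depends on an earlier video. That leaves 4 of 9 knowledge and 4 of 8 child-behavior assessments restricted to mothers who received that cycle's video.

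**Step 2: how far receivers can differ from the randomized groups (illustration).** Let *m* be the share of retained mothers who miss a given video visit, equal in both arms, and *E* the effect among receivers. If the missed video does nothing for non-receivers, and nothing carries over from earlier videos, then:

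- ITT effect = (1 − *m*) × *E*
- receiver effect ÷ ITT effect = 1 / (1 − *m*)
- *m* = 0.05: 1 / 0.95 = 1.05
- *m* = 0.20: 1 / 0.80 = 1.25

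The documents do not give *m*; 5% to 20% is an assumed range. Carry-over from earlier videos brings the ratio closer to 1.

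**Step 3: if attendance differs by arm (illustration).** Suppose non-attenders improve less often than attenders by a gap *g*, the same in both arms, and the share missing differs by *d*. The complete-case difference is then off by *d* × *g*:

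- 0.05 × 0.10 = 0.005, or 0.5 percentage points
- 0.10 × 0.20 = 0.02, or 2 percentage points

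These values are also assumed. Nothing in the protocol shows that attendance will differ by arm.

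**The case against.** The best case for the plan is that the gap is narrow and the analysis has ways round it. Assignment is retained for every mother throughout. Knowledge and child behavior are also measured at Visits 2, 3 and 4 without a video gate. A mother who skips Visit 2 and returns at Visit 3 supplies both nominally three months after the 9-month form she was not sent (1 year 9 months against 2 years). Her later scores could inform an imputation model together with her attendance. Section 9.2 commits to exploring selective dropout and to sensitivity analyses, and the details of imputation normally belong in the SAP. Missed visits may also be rescheduled within two months, which reduces the number affected.

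Most of this stands, and it limits the point. Four stronger readings are tempting but not supported:

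- **That knowledge and behavior are collected only from mothers who saw the video, or cannot be analyzed by ITT at all.** The annual-visit questionnaires permit an ITT analysis with ordinary missing data.
- **That non-attenders would be imputed as though they had seen the video.** The protocol specifies no such model.
- **That the mediation analyses or the primary model are shown to be biased.** Section 9.4.3 does not say that the 1- and 9-month values are the mediators. Section 9.4.2 lists mothers' knowledge and behavior as covariates without naming time points. The caries examinations are not gated.
- **That the protocol's 21% measures the problem.** It is annual attrition, meaning dyads who leave follow-up. It is not a rate of missed visits among mothers who stay.

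What the objection does not answer is why the data should go uncollected. At the 1- and 9-month points after videos 2 and 3, every observed respondent received the video. An ITT estimate there would rest on imputing non-attenders largely from attenders, and the observed data at those points cannot test that assumption. For these endpoints the protocol offers imputation only as an option.

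**Conclusion.** The point holds for a defined part of the secondary outcomes: the 1- and 9-month assessments after videos 2 and 3. There the collection rule conditions the observed comparison on post-randomization adherence and conflicts with the ITT population in section 9.3, at time points that section 4.1 names in its hypotheses. This conclusion follows from the text and needs no assumption about rates.

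The size cannot be established from the protocol. The ratio of 1.05 to 1.25 is an illustration that rests on an assumed 5% to 20% of retained mothers missing a video visit, equal shares in both arms, no benefit from the missed video and no carry-over. The point does not depend on attendance differing by arm, which remains conjecture.

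**What to change.** In sections 5.5, 6.4 and 7.3, separate outcome collection from intervention delivery:

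- Send the 1- and 9-month knowledge and behavior questionnaires to every randomized mother who has not withdrawn, whether or not she attended the preceding video visit.
- If the visit was missed, time them from its scheduled date, which section 6.1.2 already bases on the child's date of birth.
- Analyze them by assigned group.
- Leave the rules on intervention materials after a missed visit unchanged.

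Sending the forms is not enough for the behavior endpoint. Section 9.4.3 classes each item as improved or not by comparing answers before and after the intervention, and the cycle's earlier answers are taken at the visit itself. State that, when that form is missing, the most recent answers to the same items given before the scheduled visit date serve as the earlier value. Where no such answer exists, treat the outcome as missing.

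The cost is protocol wording, a change to the REDCap trigger and the existing $20 card per extra form: 2 × $20 = $40 per missed video visit, at most 4 × $20 = $80 for a mother who misses both. The forms already go out by link, with staff contact and mailed paper copies as backup. Some of these mothers will not respond, and for those who do, the earlier behavior value will be older than for attenders.

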6.5 CONCOMITANT THERAPY

Brief booster messages to help mothers overcome the difficulties of adopting the suggested behaviors will be sent via email and/or text link using REDCapTM at three-month follow-up after they view the videotaped messages at visits 1, 2 and 3. The booster messages for mothers of Group 1 will be autonomous-supportive, while neutral for mothers of Group 2.

6.5.1 RESCUE PROCEDURES

Mothers of children diagnosed with caries during the dental exam will be given a list of local dentists to further address their restorative needs. In the course of the children's clinical exams, unexpected conditions might be identified (e.g., dental caries, acute infection, etc.). Should this occur, mothers will be given the following options: 1) to have their children evaluated on the same day on an emergency basis at the UI Department of Pediatric Dentistry, 2) to follow up with their respective local dental providers, or 3) to follow up with the UI Department of Pediatric Dentistry; appointments will be made within 1-4 weeks for further assessment and appropriate treatment. The clinical situation will dictate the urgency of the follow-up care. For example, participants with acute abscess will be strongly encouraged to receive immediate evaluation (e.g., urgent care clinic at UI Department of Pediatric Dentistry or same day visit with their local dentists). Participants with a condition that does not require immediate attention (i.e., asymptomatic dental caries, etc.) could have a longer wait period (e.g. follow up in 4 weeks). In the event that participants decide to follow up with their local dentists, they will be offered the option of a typed document detailing any concerns and oral exam findings. Otherwise, all information collected by the study will be de-identified and not shared with any outside sources.

7 STUDY INTERVENTION/EXPERIMENTAL MANIPULATION DISCONTINUATION AND PARTICIPANT DISCONTINUATION/WITHDRAWAL

7.1 DISCONTINUATION OF STUDY INTERVENTION/EXPERIMENTAL MANIPULATION

This study may be temporarily suspended or prematurely terminated if there is sufficient reasonable cause. Written notification, documenting the reason for study suspension or termination, will be provided by the suspending or terminating party. If the study is prematurely terminated or suspended, the PI will promptly inform study participants of changes to study visit schedule, the IRB and NIDCR, and will provide the reason(s) for suspension or termination.

Circumstances that may warrant termination or suspension include, but are not limited to:

- Determination of unexpected, significant, or unacceptable risk to participants
- Demonstration of efficacy that would warrant stopping
- Insufficient compliance of study staff to the protocol (i.e., significant protocol violations)
- Data that are not sufficiently complete and/or evaluable
- Determination that the primary endpoint has been met
- Determination of futility.

The study may resume once concerns about safety, protocol compliance, and data quality are addressed, and satisfy the funding agency, IRB or other relevant regulatory or oversight bodies.

